### **V0**

A trained research assistant will screen potentially eligible patient's in-person to see if they further qualify to participate. Every patient will be asked if they have access to wireless internet at home and their vision will be tested. A patient must be able to see at least 20/50 in one eye to be eligible to participate.

- Vision Assessment with Snellen Chart
  - o Chart should be two chart lengths away from participant
  - o Ask participant to cover their right eye and use their left eye to read the smallest line they can from the chart
  - o Ask participant to cover their left eye and read the smallest line they can with their right eye
  - o Administrator should follow patient's reading on a copy of the chart included in forms
  - o Record acuity in right and left eyes
  - o If vision is not better than 20/50 in at least one eye, the patient is ineligible to participate in the study.

### **Study Schema**

	Screening V0	Baseline (in person)	Ongoing (30d)	30d Follow-Up (in-person or phone call)	90d Post- Enrollment
Informed Consent	X				
Vision Assessment	X				
Participant Data Collection:					
Self-reported demographics		X			
Self-reported health care utilization		X		X	
Respiratory symptoms/morbidity		X		X	
Quality of Life		X		X	

Health Literacy Assessment		X			
Spirometry		X		X	
SpiroPD device education		X			
SpiroPD use survey		X		X	
Reminder Text/Phone calls			X		
Device Data Collection			X		
Medical Record Data Collection		X	X	X	X

### Texting and Phone Calls

A trained research assistant will use a study specific cell phone to communicate with patients. Patients will only be contacted by phone or text if they have given research staff permission during enrollment and provide the number to call and/or text. Patients will be able to call us directly if they need additional assistance with the device or have any questions. In addition, if the patient had been seen by our COPD APNs in the hospital and make us aware that he or she is not feeling well the research assistant will get in touch with the APN from our COPD program to ensure this information gets communicated to them. We will reach out to patients to offer additional technical support (at 7 days) and to remind them of their 30 day follow up (prior to their appointment). Patient phone numbers will be stored in the phone using a study ID number. We will not store any other identifiable information in the cell phone..

### Device Data Collection

The SpiroPD device will record participant use and lung function scores. These measurements are stored in a HIPAA compliant server over wifi and are available to the participant and research team.

### Survey Data Collection

Trained research staff will assess the following at the initial enrollment, post-discharge follow-up visit (for hospitalized patients), and at the 30-day follow-up:

- Demographics
- Self-reported health care utilization
- respiratory symptoms/morbidity
  - o Modified Borg Dyspnea Scale
  - o Modified Medical Research Council (MMRC) Dyspnea Scale
  - o COPD Assessment Tool
- Self-reported medication adherence
  - o MARS
- Quality of Life
  - o St. George's Respiratory Questionnaire-COPD
- Health Literacy: Ask brief health literacy screen questions for all participants
  - Brief Health Literacy Screen (BHLS) – three questions
    - o How often do you have problems learning about your medical condition because of difficulty understanding written information?
    - o How confident are you filling out medical forms by yourself?

- How often do you have someone help you read hospital material?
- SpiroPD use
  - SpiroPD Pre-Education Survey
  - SpiroPD Post-Education Survey
  - SpiroPD Follow-Up Survey
  -
- Assess vision with Snellen Chart
  - Chart should be two chart lengths away from participant
  - Ask participant to cover their right eye and use their left eye to read the smallest line they can from the chart
  - Ask participant to cover their left eye and read the smallest line they can with their right eye
  - Administrator should follow patient's reading on a copy of the chart included in forms
  - Record acuity in right and left eyes
  - If vision is not better than 20/40 in at least one eye attempt to correct vision with non-prescription glasses
    - 4 strengths of glasses: 2.00, 2.25, 2.75, and 3.25
    - Start with 2.00, and repeat the vision screen, with each eye separately
    - If visual acuity of 20/40 is reached in at least one eye, the patient is eligible to complete the STOHFLA HL evaluation using the readers
  - If vision is not corrected after trying all of the strengths of the readers, the patient is ineligible to complete the STOHFLA HL evaluation

## **Spirometry**

Spirometry will be performed using the portable KoKo spirometer and the SpiroPD device. We have previously demonstrated that this population has poor perception of airflow obstruction and spirometry is feasible during the inpatient setting.

## **Medical Record and Administrative Data Collection**

The following data will be collected by the CRDW and merged with survey and device data:

- Admission labs (e.g., bicarbonate, hemoglobin, creatinine) (hospitalized patients)
- Admission and discharge medications, inpatient medications (hospitalized patients)
- Admission length of stay (hospitalized patients)
- Admit and discharge service (hospitalized patients)
- Procedures during hospital stay (ICD-10 coded procedure) (hospitalized patients)
- Index admission type (urgent or emergent vs elective) (hospitalized patients)
- Comorbidities, ICD-9 & ICD-10
- Number of ED visits in the 12 months prior to enrollment and during the study period
- Number of hospitalizations in the 12 months prior to enrollment and during the study period
- Number and type of outpatient visits in the 12 months prior to enrollment and during the study period

- Number of observation stays in the 12 months prior to enrollment and during the study period
- PFTs
- Prescriptions for medications
- EPIC Healthy Planet data, including follow up phone calls, medication education, etc
- Consults received
- Insurance types
- Cost accounting system data (eSimon) including expected pay, net expected pay, etc.

These data will be collected from the time of electronic medical record initiation at University of Chicago (11/1/2008) until 90 days past enrollment.

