## PURPOSE & HYPOTHESIS

Our central hypotheses are that handheld spirometry is feasible for inpatient and at-home use and is equally efficacious at determining lung function when compared with bedside spirometry measurements. To test these hypotheses, we propose the following specific aims:

**Specific Aim 1:** Determine the correlation of SpiroPD handheld spirometry measurements with bedside Koko spirometry lung function.

**Hypothesis:** Correlation between the two lung function tests will be substantial for both hospitalized and ambulatory patients.

**Specific Aim 2:** To determine the feasibility, adherence, and preliminary management efficacy of home SpiroPD testing.

**Hypotheses:** (1) Patients will demonstrate substantial adherence to daily home spirometry testing; (2) medication adherence will increase significantly in patients who are adherent to daily home spirometry testing; (3) acute care utilization will decrease significantly in adherent patients.

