### Inpatient enrollment

Hospitalized patients with COPD will be screened using medical records. A member of the patients' inpatient care team (e.g., primary team, pulmonary consult service, COPD service) will be contacted for assent prior to approaching the patient. After consent, a trained research assistant will approach the patient and do the screening visit (V0) to ensure the patient has wireless internet and sufficient vision to see if they are eligible to continue with the remaining study visits. The research assistant will conduct both KoKo and SpiroPD spirometry with the participant no earlier than day 2 of the hospitalization. During this assessment, the research assistant will also provide the participant with training on use and function of the SpiroPD

device. They will return for a research visit at 30 days (+/- 1 week) if no clinic visit is scheduled during the 30 day research visit window. The patient will be offered a CTA/bus pass to return for their 30 day follow up. If the study participant is unable to attend the study visit in-person, we will arrange a phone call.

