## **DURATION**

Participants will be asked to use the SpiroPD device for 30 days after discharge from the hospital or starting the day after the clinic visit if recruited from clinic. They will be in the study for 30 days (with a window of +/- 1 week for the 30 day visit) from the time of enrollment.

Electronic data will be collected from the time of electronic medical record initiation at University of Chicago (11/1/2008) until 90 days past the day of enrollment.

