## STATISTICAL ANALYSES

**SA1:** Correlation between KoKo and SpiroPD measurements will be assessed using Spearman's correlation coefficient. A high correlation ( $> 0.8$ ) will demonstrate the usefulness of the SpiroPD device in these patients.

**SA2:** Feasibility process measures such as proportion of participants who adhere to the at-home use of SpiroPD lung function testing, adherence measures to treatment regimens, and estimates of efficacy as denoted by exacerbations and acute care utilization will be analyzed using descriptive statistics. Patient characteristic associated with increased SpiroPD use, treatment adherence, and efficacy of lung function testing will use McNemars, Fishers exact or Chi square testing for categorical variables and rank sum or t-tests for continuous variables.

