## **DATA SHARING**

A summary final report will be provided to the SpiroPD manufacturer. Individual level data will not be provided. The final report should include de-identified summary data for those receiving a SpiroPD device:

- Used SpiroPD Y/N
- If Y—usage data (# of uses)
- If Y—lung function data from SpiroPD
- If Y-- Medication adherence from SpiroPD
- Gender
- Age
- Pre/post study health care utilization
- Insurance type
- Demographics

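### Pre/post acute care use has no defined after window, rate scale, comparator or index-admission rule; compared as collected, counts fall about 75% to 92% with no effect

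*Combined protocol and SAP*

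**What the plan says.** - Under Purpose & Hypothesis, hypothesis (3) of Aim 2 is that "acute care utilization will decrease significantly in adherent patients". It does not say whether the decrease is relative to the same patients' past or to non-adherent patients.
- Medical Record and Administrative Data Collection lists "Number of hospitalizations in the 12 months prior to enrollment and during the study period". ED visits, outpatient visits and observation stays are listed over the same two periods. Index admission type and length of stay are separate items.
- The after period has two possible lengths. Duration says of participants: "They will be in the study for 30 days (with a window of +/- 1 week for the 30 day visit) from the time of enrollment". It also says that electronic data are collected "until 90 days past the day of enrollment".
- For inpatients, Duration adds another clock: "Participants will be asked to use the SpiroPD device for 30 days after discharge from the hospital". This starts later than a clock that runs from enrollment.
- Under Inpatient enrollment, patients are recruited while hospitalized, and the paired spirometry is done "no earlier than day 2 of the hospitalization".
- Statistical Analyses (SA2) says that "estimates of efficacy as denoted by exacerbations and acute care utilization will be analyzed using descriptive statistics". It then lists McNemar, Fisher, chi-square, rank-sum and t-tests for patient characteristics associated with device use, treatment adherence and efficacy. It does not say what McNemar's test would pair.
- Data Sharing lists "Pre/post study health care utilization" among the items of the final report, with no window lengths.
- The Study Schema also has self-reported utilization at baseline and at 30 days, with no stated recall period.

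**The concern.** A before/after utilization result is clearly intended, since a decrease is hypothesized and a pre/post item is promised for the report. The only utilization measure with a stated before window is the 12-month record count. The matching after count covers a much shorter time, and nothing in the plan puts the two on a common scale.

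A second problem is specific to inpatients. Their index admission begins before enrollment, so a 12-month look-back that dates stays by admission picks it up. Clinic recruits have no such qualifying event. Converting to rates does not remove this extra event, so the two problems need two separate rules, and the plan has neither.

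The study is a pilot meant to support further studies and grant applications. An apparent fall in admissions that comes from the windows could be carried forward as preliminary efficacy. No control arm is described that would reveal it.

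**Working it through.** The documents give no utilization rate, power or sample size for this outcome, so there is no figure of the plan's own to reproduce. The check asks what the collected counts would show if nothing changed.

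**Inputs**
- Before window: 12 months, taken as 365 days (Medical Record and Administrative Data Collection).
- After window: 30 days, or 23 to 37 days with the visit window, or 90 days (Duration).
- n = 150 (Type and Number of Experimental Subjects). The inpatient/outpatient split is not stated.
- Admission rate L per patient-year: an assumption, constant over time, shown at 0.5, 1 and 2.

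**Step 1: window length alone, index stay not counted.** Before = L; after = L × d/365; ratio = d/365, whatever the value of L.
- 30 days: 30/365 = 0.082, a fall of 91.8%.
- 90 days: 90/365 = 0.247, a fall of 75.3%.
- 23 to 37 days: 0.063 to 0.101, a fall of 93.7% to 89.9%.

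McNemar's test on any admission before versus after shows what a paired test would do with these windows. In a Poisson simulation (n = 150, 4,000 runs, no effect, index stay excluded, L = 0.5 to 2), it declared a significant decrease in at least 99.9% of runs for both the 30-day and the 90-day window.

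**Step 2: inpatients, index stay dated by admission and so counted as before.** Before = L + 1; after rate = L per year. Annualised ratio = L/(L + 1). Raw ratio = (L × d/365)/(L + 1).

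| Assumed L | Annualised ratio | Raw ratio, 30 days | Raw ratio, 90 days |
|---|---|---|---|
| 0.5 | 0.5/1.5 = 0.33 | 0.041/1.5 = 0.027 | 0.123/1.5 = 0.082 |
| 1 | 1/2 = 0.50 | 0.082/2 = 0.041 | 0.247/2 = 0.123 |
| 2 | 2/3 = 0.67 | 0.164/3 = 0.055 | 0.493/3 = 0.164 |

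In a cohort with inpatient share f, the annualised ratio is L/(L + f). At f = 0.5 it is 0.50, 0.67 and 0.80 for L = 0.5, 1 and 2. With no inpatients it is 1.00.

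**Step 3: when the inpatient artefact disappears.** The annualised ratio returns to 1 when the post-discharge rate is (L + 1)/L times background: 3.0 times at L = 0.5, 2.0 at L = 1, 1.5 at L = 2. Above that, the comparison shows an increase.

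**Step 4: the other dating rule.** The index stay straddles enrollment. Dated by discharge it falls in the after window. At L = 1 the raw counts are then 1 before and 1 + 30/365 = 1.08 in 30 days, and the annualised after rate is 1.08 × 365/30, about 13 per year. The direction therefore depends on a dating rule that the plan does not state.

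**Step 5: after correction.** With the index stay out of both windows and events divided by person-time, the no-effect ratio under a constant rate is L/L = 1.00 for either after window.

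**The case against.** The strongest reply is that the plan does not prescribe this comparison. The 12-month count appears in a list of variables to extract, SA2 promises only descriptive statistics, and Data Sharing gives no method. Hypothesis (3) can be read as adherent versus non-adherent patients over the same after period. Most of the tests named in SA2 are between-group tests, and an admission before enrollment would not enter that contrast. Baseline self-report offers another before measure. Records reach back to 11/1/2008, so matched windows can be built. The index stay can be identified from its own items.

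All of this stands as a limit on the claim. A reader might infer that the trial will compare raw counts, that every inpatient's index stay must fall in the before count, and that a decrease is therefore guaranteed. The documents do not support that. No section calls for a raw-count comparison, the placement of the index stay depends on the dating rule, and outpatients are unaffected by it. The Background frames the study around early readmission, so a raised post-discharge rate is a realistic alternative to the constant rate assumed here.

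The gap remains all the same. That rates could be computed, or the index stay filtered out, shows only that a correction is feasible, not that it is planned. The self-report item has no recall period. The pre/post item in the report remains even if hypothesis (3) is a between-group comparison.

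**Conclusion.** The concern holds in a conditional form. The plan commits to a pre/post utilization result and predicts a decrease, but leaves the after window, rate scale, comparator and index-stay handling undefined.

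- If the counts are compared as collected, a fall of about 92% (30 days) or 75% (90 days) is expected with no effect. This assumes only a constant rate and does not need the index-stay argument.
- If rates are used but the index stay is dated by admission and kept, the inpatient no-effect rate ratio is 0.33 to 0.67 for assumed rates of 0.5 to 2 per year. This is diluted by the unknown outpatient share. It is cancelled or reversed by a post-discharge rate 3.0 to 1.5 times background.

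The direction on the rate scale is thus not fixed. This goes beyond missing detail, because the windows as stated give a misleading answer to a stated hypothesis. Utilization is one part of a preliminary-efficacy aim in a pilot, so it should be settled before analysis but does not threaten Aim 1.

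**What to change.** Add to Statistical Analyses:

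1. Exclude the index stay and its ED visit from both windows.
2. End the 12-month before window on the day before the index admission (inpatients) or the clinic visit (outpatients). Start the after window at discharge or the clinic visit.
3. Name 30 or 90 days as the main after window. Records stop 90 days past enrollment, so a window that starts at discharge must be cut there. A full 30 days is covered if discharge is within 90 − 30 = 60 days of enrollment.
4. Analyse events per person-day and report by enrollment setting.
5. State whether hypothesis (3) is a within-patient comparison or adherent versus non-adherent over the same after window.
6. Describe any uncontrolled pre/post change as descriptive, not as evidence of efficacy. Even with rules 1 to 4, a raised post-discharge rate would show as an increase.

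Duration should also reconcile the 30 days counted from enrollment with the 30 days of device use counted from discharge.

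The cost is some SAP wording, a date filter and a little more analysis, with no new data collection. The apparent reduction will be smaller, or may become an increase.

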## **DURATION**

Participants will be asked to use the SpiroPD device for 30 days after discharge from the hospital or starting the day after the clinic visit if recruited from clinic. They will be in the study for 30 days (with a window of +/- 1 week for the 30 day visit) from the time of enrollment.

Electronic data will be collected from the time of electronic medical record initiation at University of Chicago (11/1/2008) until 90 days past the day of enrollment.

## **LOCATION**

The study will take place at the University of Chicago Medicine within the hospital and the clinic.

## **TYPE AND NUMBER OF EXPERIMENTAL SUBJECTS**

We will enroll 150 study participants.

### **Inclusion Criteria**

1. Age 18 years and older
2. Physician-diagnosed COPD. We will enroll patients even if the primary reason for admission is not COPD or asthma (e.g., patients admitted for heart failure, but with a physician diagnosis of COPD are eligible).
3. Able to perform spirometry
4. Access to wireless internet at home
5. Visual acuity of at least 20/50 in one eye

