### **Exclusion Criteria**

1. Currently in an intensive care unit
2. Physician declines to provide consent
3. Patient unable to provide consent (e.g., history of cognitive impairment, unable to understand English) or declines to provide consent

For our study regarding correlation of the Koko with the SpiroPD devices to measure lung function, we will have power to detect a small to moderate effect size ( $p=0.023$ ) at  $>80\%$  ( $87\%$ ) power with  $n=150$  participants at an alpha  $<0.05$ .

Statistical Test (Spearman)	Sample Size	Power	Correlation	Significance Level
Correlation	193.78	0.8	0.2	0.05
Correlation	145.92	0.8	0.23	0.05
Correlation	123.13	0.8	0.25	0.05
Correlation	84.75	0.8	0.3	0.05

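### Entry on a physician diagnosis without an airflow result may widen the lung-function range and, for a borderline device, lift the pooled Spearman past 0.8; a sensitivity analysis in obstructed participants would show whether it does

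*Combined protocol and SAP*

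**What the plan says.** All references are to the combined protocol and SAP.

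- **Inclusion Criteria.** Entry requires "Age 18 years and older", a diagnosis given by a physician ("Physician-diagnosed COPD. We will enroll patients even if the primary reason for admission is not COPD or asthma") and being "Able to perform spirometry". The last asks for the ability to do the test, not for any result. Patients admitted for another reason, such as heart failure, are expressly eligible.
- **Exclusion Criteria.** These cover intensive care ("Currently in an intensive care unit"), refusal by the physician, and inability or refusal to consent. None concerns absence of airflow obstruction.
- **Statistical Analyses, SA1.** "Correlation between KoKo and SpiroPD measurements will be assessed using Spearman's correlation coefficient", and a value above 0.8 "will demonstrate the usefulness of the SpiroPD device in these patients". The spirometric parameter is not named. No subgroup, confidence interval or agreement statistic is planned.
- **Purpose & Hypothesis, Aim 1.** "Correlation between the two lung function tests will be substantial for both hospitalized and ambulatory patients".
- **Data available.** KoKo readings are taken at baseline for inpatients and obtained from the clinic visit for outpatients. PFTs are also extracted from the record.

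**The concern.** With a given measurement error, two devices correlate more strongly in a sample with a wide range of true lung function than in one with a narrow range. Participants who carry the label but are not obstructed would tend to sit at the upper end of the range. Adding them can raise the pooled coefficient with no change in how well SpiroPD measures.

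The 0.8 benchmark is the only success criterion for Aim 1. The Background presents the study as the first validation of the device in COPD and as the basis for later studies and grant applications. If the coefficient passed 0.8 only because of the mix of participants, the conclusion would be weaker for obstructed patients than it appears. The plan has the data to check this but does not say that it will.

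**Working it through.** **1. The plan's own figure.** The power table uses a Fisher-z calculation against zero correlation: n = ((z₀.₉₇₅ + z₀.₈₀)/atanh(r))² + 3. For r = 0.23 this is ((1.960 + 0.842)/0.2342)² + 3 = 146.1, against 145.92 in the table. The other rows reproduce equally well (193.97, 123.32 and 84.93 against 193.78, 123.13 and 84.75). The calculation concerns correlation = 0, so it says nothing about the 0.8 benchmark or about this point.

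**2. Why spread matters.** If both devices read the true value (SD s) with independent errors (SDs e₁, e₂), the Pearson correlation is r = s²/√[(s² + e₁²)(s² + e₂²)]. For normal data Spearman = (6/π)·arcsin(r/2).

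**3. Illustration A.** Every input is an assumption, because the documents give none:
- obstructed FEV1: mean 1.2 L, SD 0.45
- non-obstructed FEV1: mean 2.3 L, SD 0.60
- error SD: SpiroPD 0.36 L, KoKo 0.08 L

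Obstructed only: s² = 0.2025, so r = 0.2025/√[(0.2025 + 0.1296)(0.2025 + 0.0064)] = 0.2025/0.2634 = 0.769, and Spearman = 0.754.

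With 20% non-obstructed, the pooled s² = 0.8(0.2025) + 0.2(0.36) + 0.8(0.2)(1.1²) = 0.428, roughly double. The mixture is not normal, so the pooled Spearman is simulated (300,000 patients per scenario). The last column is the chance that the observed pooled value exceeds 0.8 at the planned size ("We will enroll 150 study participants").

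| Non-obstructed share | Pooled Spearman | Obstructed only | Chance observed > 0.8, n = 150 |
|---|---|---|---|
| 0% | 0.75 | 0.75 | about 9% |
| 10% | 0.80 | 0.75 | about 48% |
| 20% | 0.84 | 0.75 | about 85% |
| 30% | 0.87 | 0.75 | about 98% |
| 40% | 0.89 | 0.75 | not computed |

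The 95% limits of agreement are ±1.96·√(0.36² + 0.08²) = about ±0.72 L in every row: the device is the same throughout.

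**4. Varying the other inputs of A.**
- SpiroPD error SD 0.15, 0.20, 0.25 or 0.30 L: obstructed-only Spearman is 0.93, 0.89, 0.85 or 0.81. The benchmark is met without any non-obstructed participants.
- Error SD 0.45 L, 20% non-obstructed: pooled 0.78. It fails both ways.
- With 20% non-obstructed, the verdict changes only for error SDs of roughly 0.31 to 0.42 L.
- Obstructed SD 0.55 L instead of 0.45 L: obstructed-only 0.82, so no change of verdict.
- Non-obstructed mean 1.6 L (gap 0.4 L): pooled 0.77, 0.79 and 0.799 at 10%, 20% and 30%. It stays below 0.8.
- SpiroPD error proportional to volume (30%): pooled about 0.77, 0.80 (just under) and 0.81 at 10%, 20% and 30%.

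**5. Illustration B, a separate grid.** Obstructed FEV1 mean 1.3 L, SD 0.5; both devices with the same error SD (0.27 to 0.37 L); obstructed-only Spearman about 0.63, 0.70, 0.745 or 0.765; shares of 5, 10, 20, 30 and 40%; three non-obstructed distributions. That is 4 × 5 × 3 = 60 scenarios.

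| Non-obstructed mean (SD) | Scenarios with pooled > 0.8 |
|---|---|
| 2.4 L (0.6) | 10 of 20 |
| 2.0 L (0.6) | 5 of 20 |
| 1.6 L (0.5) | 0 of 20 |

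In total 15 of 60 cross. Crossing needs a mean gap of about 0.7 to 1.1 L and, in most cases, a share of at least 10% to 30%. With a 0.3 L gap the pooled value rises by only about 0.02.

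**The case against.** The strongest reply is that the plan defines its population openly. The Methods Overview speaks of patients diagnosed with COPD in hospital and clinic, broad entry is deliberate, and this is a single-center pilot. On that reading the pooled coefficient answers the question asked. This stands, and is why the pooled analysis should stay.

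A second reply is that lower correlation among obstructed patients need not mean poorer measurement. In the models with constant error it is purely the effect of a narrower range. Demanding more than 0.8 in that subgroup would keep a spread-dependent criterion and could fail a device whose error is unchanged. This also stands: the subgroup should be reported, not made the condition for success, and limits of agreement should accompany it because they depend less on range.

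Three stronger readings are tempting, and the documents do not support them:
- A reader might infer from the Background that COPD diagnoses in this population are known to be unreliable. It says that spirometry is often not done in acute exacerbations and that this leads to errors in judging severity. It does not say that diagnoses are wrong, so participants *may* be non-obstructed; it is not shown that some *will* be.
- A reader might infer that airflow is never checked. That is true of eligibility only, since KoKo readings exist at baseline.
- A reader might infer that the benchmark would be passed because of non-obstructed patients. That needs a share, a distribution and a device error that the documents do not give.

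**Conclusion.** The point holds as a possibility that the plan leaves unexamined. Entry requires no airflow result, SA1 pools everyone, and the benchmark is a statistic that moves with the spread of the sample. For a device whose coefficient in obstructed patients is about 0.70 to 0.77, a non-obstructed share of roughly 10% to 30% or more with mean FEV1 0.7 to 1.1 L higher could carry the pooled value past 0.8. For a clearly better or clearly worse device, or with a gap of 0.3 to 0.4 L, the verdict does not change in the scenarios examined at shares up to 30%. All of this assumes that FEV1 is the parameter, which SA1 does not state. It is a cheap improvement, not a flaw that invalidates Aim 1.

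**What to change.** Keep the eligibility criteria and the pooled SA1 analysis. Add to SA1:

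1. The spirometric parameter or parameters to be compared.
2. The number and proportion of participants not obstructed on baseline KoKo FEV1/FVC. The team should fix the cut-off before the data are examined, as the documents give none.
3. A pre-specified sensitivity analysis in obstructed participants, giving the Spearman coefficient with its 95% confidence interval and the Bland-Altman limits of agreement. Giving the limits for the pooled sample as well would allow comparison.
4. A rule for wording: if the coefficient is not above 0.8 in obstructed participants, the conclusion is stated as applying to physician-diagnosed COPD only.

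The cost is one extra analysis on spirometry already collected, with fewer pairs. Taking the interval as tanh(atanh(0.80) ± 1.96·√(1.06/(n − 3))), an observed 0.80 has a 95% interval of 0.73 to 0.85 at n = 150. If 20% are not obstructed, n = 0.8 × 150 = 120 and the interval is 0.72 to 0.86, only slightly wider.
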